APPENDIX – IV

Data Collection Sheet

Title of the Study:

Free Breathing versus Deep Inspiration Breath Hold Technique in Adjuvant Radiotherapy for Left Sided Breast Cancer: A Dosimetric Comparison of Target Volumes, Heart and Left Lung

Principal investigator: [name]

Section A: Participants Personal Information

ID No:

S.N.	Questions	Options	Code	Skip
01.	What is your age?	  years		
02.	What is your religion?	Islam -1 Hinduism-2 Christianism-3 Buddhism-4 Others-0		
03.	What is your educational status?	Illiterate-1 Below primary-2 Above primary up to SSC-3 HSC-4 Graduate-5 Post graduate-6 Others-0		
04.	What is your Occupation?	Student-1 Housewife-2 Service holder-3 Business-4 Others-0		
05.	Age at menarche	  Years		

06.	What is your marital status?	Unmarried-1 Married-2 Widowed-3 Separated-4		For code 1 skip question No.6
07.	Age at marriage?	  years		
08.	Age at 1 st pregnancy?	  years		
09.	Did you breastfeed your children?	Yes-1 No-2		
10.	Are you menopausal?	Yes-1 No-2		For code 2 skip question No.09
11.	Age at menopause?	  years		
12.	Do you have any history of using OCP?	Yes-1 No-2		For code 2 skip question No.11
13.	Duration of using OCP	  years		
14.	Do you have any history of using HRT?	Yes-1 No-2		For code 2 skip question No.13
15.	Duration of using HRT	  years		
16.	Do you have any family history of cancer? (mention if any)			
17.	Comorbidity (if any)			

সেকশন-এ: অংশগ্রহনকারীর ব্যাক্তিগত তথ্যসমূহ

আইডি:

নং	প্রশ্ন	উত্তর	কোড	বাদ
১.	আপনার বয়স কত?	 বৎসর		
২.	আপনি কোন ধর্মের অনুসারী?	ইসলাম-১ হিন্দু-২ ধ্বিষ্ঠান-৩ বৌদ্ধ-৪ অন্যান্য-০		
৩.	আপনার শিক্ষাগত যোগ্যতা কি?	অশিক্ষিত-১ প্রাথমিক পর্যন্ত-২ প্রাথমিক থেকে এসএসসি পর্যন্ত -৩ এইচএস সি -৪ গ্র্যাজুয়েট -৫ পোস্ট গ্র্যাজুয়েট-৬ অন্যান্য -০		
৪.	আপনার পেশা কি?	ছাত্র/ছাত্রী-১ গৃহিণী-২ চাকুরিজীবি-৩ ব্যবসায়ী-৪ অন্যান্য -০		
৫.	কত বছর বয়স থেকে আপনার রাজক্রিয়া শুরু হয়েছিল?	 বৎসর		
৬.	আপনার বৈবাহিক অবস্থা কি?	অবিবাহিত-১ বিবাহিত-২ বিধবা -৩ বিবাহবিচ্ছেদ-৪	কোড ১ এর জন্য ৭ নং প্রশ্ন বাদ	
৭.	বিবাহ কালে আপনার বয়স কত ছিল?	 বৎসর		

৮.	প্রথম সন্তান জন্মের সময় আপনার বয়স কত ছিল?	  বৎসর		
৯.	আপনি কি আপনার বাচ্চাকে বুকের দুধ খাইয়েছিলেন?	হ্যা ১ না ২		
১০.	আপনার কি মাসিক একেবারে বন্ধ হয়ে গেছে?	হ্যা ১ না ২		কোড় ২ এর জন্য ১১ নং প্রশ্ন বাদ
১১.	কত বছর থেকে মাসিক বন্ধ আছে?	  বৎসর		
১২.	আপনি কি জন্ম বিরতিকরণ পিল খেয়েছেন কখনো?	হ্যা ১ না ২		কোড় ২ এর জন্য ১৩ নং প্রশ্ন বাদ
১৩.	আপনি কতদিন জন্ম বিরতিকরণ পিল খেয়েছেন	  বৎসর		
১৪.	মাসিক বন্ধ হওয়ার পরে কোনো হরমোনের ট্যাবলেট খেয়েছেন?	হ্যা ১ না ২		কোড় ২ এর জন্য ১৫ নং প্রশ্ন বাদ
১৫.	আপনি কতদিন হরমোনের ট্যাবলেট খেয়েছেন	  বৎসর		
১৬.	জানামতে পরিবারের কারো কোন ক্যান্সার রোগ ছিল কি না? (থাকলে বিবরণ)			
১৭.	আপনার ডায়াবেটিস, উচ্চরক্তচাপ, কিডনী বা অন্যান্য দীর্ঘমেয়াদী সমস্যা আছে কিনা? থাকলে কোনটি?			

Section B: Clinical Examination Findings**ID No:****i. General and Local Examination:**

Serial No	General examination	Option	Code
01.	Performance status		
02.	Body-weight (in kg)	 	
03.	Height (in cm)	  	
04.	Body mass index (in kg/m ²)	 kg/m ²	
05.	Anemia	Yes-1 No-2	
06.	Jaundice	Yes-1 No-2	
07.	Edema	Yes-1 No-2	
08.	Dehydration	Yes-1 No-2	
09.	Palpable lymph node (if yes, mention site)	Yes-1 No-2	
10.	Body temperature		
11.	Breast examination		
12.	Others		

ii. Systemic Examination:**01. Respiratory system examination****02. Cardiovascular system examination**

Section C: Findings of Investigations ID No.

i. Imaging Test

- Chest xray PA view
- ECG
- Echocardiography
- Lung function test

ii. Histopathological Examination:

- Tumor size
- Nodal involvement
- Histopathological variety
- Grade

iii. Immunohistochemistry:

- Estrogen receptor, ER
- Progesterone receptor, PR
- HER-2 receptor

Section D: Previous Treatment ID No:

- Chemotherapy: Neoadjuvant Adjuvant
- Regimen of chemotherapy with doses:

- Number of cycles:
- Date of completion:
- Date of surgery:
- Duration from surgery or chemotherapy: (whichever is shorter)

Section E: Treatment Delivery ID No:

Technique of Irradiation	Arm	Code
IMRT with FB technique	Arm A =1	
IMRT With DIBH technique	Arm B = 2	

Section F: Radiation Doses**ID No:**

- Planning target volume
 - Total volume
 - Maximum dose, D_{\max}
 - Mean dose, D_{mean}
 - V_{95} of PTV
- Heart
 - Mean heart dose, D_{mean}
 - Maximum heart dose, D_{\max}
 - V_{25} of heart
- Left lung
 - Mean dose to left lung, D_{mean}
 - V_{20} of left lung

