In BSMMU, data acquired by CT scanner and sentinel will be transferred to central database for automatic tracking of same surface points and breathing pattern with a Catalyst™ system in the treatment room during every fraction, without any manual intervention. IMRT planning will be done by Monaco® Treatment Planning Software (TPS) 5.11 (Elekta AB, Stockholm, Sweden) consist of 6 MV tangential beams.

In other institutes, data will be imported to console automatically from RGSC and RPM™ and a treatment gate window will be established. IMRT planning will be done using TPS Eclipse v15.1 (Varian Medical Systems, Palo Alto, CA, USA) in CMH and v16.1 in Lab aid.

Plans will be evaluated using dose constraint as MSKCC dosimetric planning guidelines for breast IMRT: for heart- $V_{25Gy} < 25\%$, mean dose, $D_{mean} < 20Gy$, maximum dose, $D_{max} \leq 53$ Gy; for lungs- $V_{20Gy} \leq 30\%$, mean dose, $D_{mean} \leq 22$ Gy.

Case Collection

From the OPD of study centres, a total of 50 participants will be recruited after justifying inclusion and exclusion criteria. Before participating in the study, written informed consent will be taken from each selected participant. Interviews will be taken focusing their medical and relevant history by the researcher and will be documented in the preformed data-sheet in respected department with proper privacy. Also, necessary clinical examinations and investigations will be done. Many left sided post mastectomy patients come to these centres regularly for PMRT from all over Bangladesh. Therefore, it will be easy to enrol an adequate number of participants.

Pre-treatment Evaluation

Following procedures will be done to evaluate the participant's condition before treatment:

General examination:

- Complete history, performance status and general physical examination including supraclavicular lymph nodes.

Local examination:

- Right breast examination including draining lymph node areas.
- For left side, chest wall, scar and axilla.

Systemic examination:

- Respiratory system examination.
- Cardiovascular system examination.

Investigations:

- Plain chest radiograph PA view
- ECG
- Echocardiography
- Lung function test

Along with these, all pre surgical imaging and reports will be thoroughly checked.

Intervention

All participants will receive RT with Elekta Versa HD (Elekta AB, Stockholm, Sweden) machine in BSMMU and Varian TrueBeam (Varian Medical Systems, Palo Alto, CA, USA) in other institutes.

Arm A: FB RT arm

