Participants will be treated with 40.05 Gy radiation, at 2.67 Gy daily single fraction, 5 days a week, for 3 weeks by IMRT in free breathing technique.

Arm B: DIBH RT arm

Participants will be treated with 40.05 Gy radiation, at 2.67 Gy daily single fraction, 5 days a week, for 3 weeks by IMRT in DIBH technique. As the sentinel (C-RAD, Uppsala, Sweden) and Varian RGSC and RPM™ system (Varian Medical System, Palo Alto, CA) is linked to the corresponding linear accelerator (LINAC), beam-hold will be automatically triggered when participant's breathing falls outside the acceptable range. It will ensure radiation delivery only at deep inspiration.

Variables

Demographic variables:

- Age
- Risk factors
 - Age of menarche
 - Age at first child birth
 - Lactation history
 - Use of oral contraceptive pill

- Age of menopause
- Use of hormone replacement therapy
- Pre-existing hypertension / diabetes mellitus
- Family history breast cancer or ovarian cancer
- Educational status
- Body mass index (BMI)

Clinical variables:

[figure not shown]
- Involved quadrant of the breast
- Histological variety
- Tumor grade
- Hormone receptor and HER-2 receptor status
- Stage of the disease
- Performance status

Study variables:

- Planning target volume
 - Total volume
 - Maximum dose, D_{max}
 - Mean dose, D_{mean}
 - V_{95} of PTV
- Heart
 - Mean heart dose, D_{mean}
 - Maximum heart dose, D_{max}
 - V_{25} of heart
- Left lung
 - Mean dose to left lung, D_{mean}
 - V_{20} of left lung

Data Collection

Findings will be recorded in data collection form (**Appendix-IV**).

Consort Flow Chart

Operational Definition

Deep Inspiration Breath Hold Radiotherapy

The approach of delivering prescribed radiation doses only during breath holding at deep inspiration is considered as deep inspiration breath hold radiotherapy.

Dose Volume Histogram

It is a graphical representation of the dose of radiation received by the critical structures or organs at risk per 2cc volume.

Intensity-modulated radiation therapy

It refers to a radiation therapy technique in which a nonuniform fluence is delivered to the patient from any given position of the treatment beam to optimize the composite dose distribution.

Mean dose

Statistical mean dose to the critical structure specified measured using predictive dose calculation algorithm integrated in the treatment planning system.

Maximum dose

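### The English and Bangla data sheets differ from each other and from the variable list at age at menopause and age at first birth, and involved quadrant has no designated field

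*Protocol*

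**What the plan says.** The Variables section of the protocol lists "Age of menopause" and "Age at first child birth" among the demographic variables, and "Involved quadrant of the breast" among the clinical variables. Under Data Collection it states: "Findings will be recorded in data collection form", meaning Appendix IV. Case Collection describes how the history is obtained: "Interviews will be taken focusing their medical and relevant history by the researcher".

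Section A of Appendix IV exists in an English and a Bangla version with the same item numbers.

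- Item 11, English: "Age at menopause". Item 11, Bangla: "কত বছর থেকে মাসিক বন্ধ আছ", that is, for how many years menstruation has been stopped.
- Item 8, English: "Age at 1 st pregnancy". Item 8, Bangla: the respondent's age when her first child was born.

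Section C takes tumour size, nodal involvement, histological variety, grade and receptor status. Section B has open entries for breast examination and for other findings. The protocol does not say which language version governs or how answers from the two are to be combined.

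**The concern.** A data sheet should collect the variables that the protocol lists, and two language versions of one sheet should ask the same thing under the same item number. Here neither version agrees with the list on both ages, and one listed clinical variable has no place on the sheet.

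What is at stake is descriptive. Specific objective 5 is to observe demographic variables, which covers the two ages. Quadrant falls outside that objective but is a listed clinical variable. If a duration is read as an age, or answers from the two versions are tabulated together without conversion, the menopause summary for the arms would be wrong. If nobody is prompted to transcribe quadrant, it may be absent when the baseline table is built.

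**Working it through.** The plan gives no figure on this point to reproduce. The check is a comparison of the variable list with the two versions of Section A and with Sections B to F.

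| Listed variable | English sheet | Bangla sheet |
|---|---|---|
| Age at menopause | Item 11: age (matches) | Item 11: years since periods stopped (differs) |
| Age at first child birth | Item 8: age at first pregnancy (differs) | Item 8: age at birth of first child (matches) |
| Involved quadrant | No item | Not in Section A; Sections B to F, which have no quadrant item, are in English only |

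**Item 11.** The Bangla sheet supplies its own comparison. Its item 5, on menarche, includes the word for age; its item 11 does not. As printed, item 11 therefore asks for a duration. Both versions label the answer in years, so the entry alone does not show which quantity was given. With assumed values, current age 55 and periods stopped at 48:

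- English answer: 48
- Bangla answer: 55 − 48 = 7
- Recovery: item 1 (current age) minus Bangla item 11 = 55 − 7 = 48

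The recovery works only if the coder knows which version was used and that the answer was a duration.

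**Item 8.** If the first pregnancy went to term, the English answer is usually lower than the listed variable by up to about one year. If it did not, the gap can be larger.

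**Quadrant.** The inclusion criteria require modified radical mastectomy, and Pre-treatment Evaluation limits the left-sided examination to chest wall, scar and axilla. The quadrant therefore cannot be found on examination. It has to come from the pre-surgical imaging and reports, which the same section says will be checked, but no field asks for it to be copied across.

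A related sign that the versions were not reconciled: the English item 10 tells the interviewer to skip item 9 (breastfeeding) for women who are not menopausal, whereas the Bangla item 10 points to item 11.

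**The case against.** The strongest reply is that little would be lost. Each age is asked correctly in one language, so if every interview used the same version, only one of the two would depart from the list and nothing would be mixed. The researcher who designed the sheet also conducts the interview and can clarify a loose question, and some women may answer the Bangla item 11 with an age anyway. Analysis of Data says that entries are checked and edited by hand, and a menopause age of 7 would stand out. Quadrant could be written in a free-text entry. None of the three variables appears in the dummy tables shown, and the Limitations section says that existing risk factors are not adjusted for, so no adjusted comparison would be distorted.

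Most of this stands, and it limits the consequence. A reader might infer that all three variables will be recorded wrongly or not at all, that every postmenopausal woman interviewed in Bangla will be misrecorded, or that quadrant will be missing for all 50 participants. The documents do not support any of these. That answers from both versions enter one field is likewise only an inference from the shared numbering.

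The reply does not remove the mismatch. Manual checking catches implausible values only by chance of their size, conversion needs the form version on record, and a free-text box does not prompt for quadrant.

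**Conclusion.** The point holds as a minor defect of the data sheet. Whichever version is used, one descriptive baseline variable is asked as something other than what the protocol lists: years since menopause on the Bangla sheet, age at first pregnancy on the English. Involved quadrant is listed but has no designated field, so it may go unrecorded.

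The size is small. The menopause answers can be recovered from current age when the version is known; the first-birth discrepancy is about a year or less for a pregnancy carried to term; and quadrant can be retrieved from pre-surgical records. The dose fields in Section F and the sample size do not depend on any of the three.

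The conclusion assumes that the sheets are used as printed and that the Bangla text of item 11 was read correctly from the file, since the reading turns on the absence of one word. The investigator can confirm this against the original form.

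**What to change.** Before the first enrolment:

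1. Reword Bangla item 11 to ask the age at which periods stopped, using the same construction as Bangla item 5.
2. Reword English item 8 to ask age at the birth of the first child.
3. Add an involved-quadrant field to Section C, to be filled from pre-surgical records.
4. In the same revision, correct the English skip numbers so that they point to the intended items.

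If any sheets are already complete, record which version was used, confirm that the Bangla item 11 answer is a duration, and then compute age at menopause as item 1 minus item 11. For completed English sheets, check item 8 with the participant where possible. Retrieve quadrant from the pre-surgical records.

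The cost is one form revision and no change to the analysis. Leaving it until later means converting answers and going back to records at four centres.

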APPENDIX-V

EASTERN COOPERATIVE ONCOLOGY GROUP (ECOG) PERFORMANCE SCALE

0	: Normal activity; asymptomatic
1	: Symptomatic; fully ambulatory
2	: Symptomatic; in bed < 50% of time
3	: Symptomatic; in bed > 50% of time; bedridden
4	: 100% bedridden
5	: Dead

APPENDIX- VI

UICC/AJCC TNM Staging for Breast Cancer- 8th edition, 2017

Primary Tumor (T)

Tx Primary tumor cannot be assessed

T0 No evidence of primary tumor

Tis (DCIS) Ductal carcinoma in situ

Tis (Paget) Paget disease of the nipple NOT associated with invasive carcinoma and/or carcinoma in situ (DCIS) in the underlying breast parenchyma

T1 Tumor ≤ 20 mm in greatest dimension

T1mi Tumor ≤ 1 mm in greatest dimension

T1a Tumor >1 mm but ≤ 5 mm in greatest dimension (round any measurement $>1.0\text{--}1.9$ mm to 2 mm)

T1b Tumor >5 mm but ≤ 10 mm in greatest dimension

T1c Tumor >10 mm but ≤ 20 mm in greatest dimension

T2 Tumor >20 mm but ≤ 50 mm in greatest dimension

T3 Tumor >50 mm in greatest dimension

T4 Tumor of any size with direct extension to the chest wall and/or to the skin (ulceration or macroscopic nodules) *

T4a Extension to the chest wall **

T4b Ulceration and/or ipsilateral macroscopic satellite nodules and/or edema (including peau d'orange) of the skin that does not meet the criteria for inflammatory carcinoma

T4c Both T4a and T4b are present

T4d Inflammatory carcinoma

* Invasion of the dermis alone does not qualify as T4.

** Invasion or adherence to pectoralis muscle in the absence of invasion of chest wall structures does not qualify as T4.

Regional Lymph Nodes- Clinical (cN)

- cNx*** Regional lymph nodes cannot be assessed (e.g., previously removed)
- cN0** No regional lymph node metastases (by imaging or clinical examination)
- cN1** Metastases to movable ipsilateral Level I, II axillary lymph node(s)
 - cN1mi**** Micro metastases (approximately 200 cells, larger than 0.2 mm, but none larger than 2.0 mm)
- cN2** Metastases in ipsilateral Level I, II axillary lymph nodes that are clinically fixed or matted; or in ipsilateral internal mammary nodes in the absence of axillary lymph node metastases
 - cN2a** Metastases in ipsilateral Level I, II axillary lymph nodes fixed to one another (matted) or to other structures
 - cN2b** Metastases only in ipsilateral internal mammary nodes in the absence of axillary lymph node metastases
- cN3** Metastases in ipsilateral infraclavicular (Level III axillary) lymph node(s) with or without Level I, II axillary lymph node involvement; or in ipsilateral internal mammary lymph node(s) with Level I, II axillary lymph node metastases; or metastases in ipsilateral supraclavicular lymph node(s) with or without axillary or internal mammary lymph node involvement
 - cN3a** Metastases in ipsilateral infraclavicular lymph node(s)
 - cN3b** Metastases in ipsilateral internal mammary lymph node(s) and axillary lymph node(s)
 - cN3c** Metastases in ipsilateral supraclavicular lymph node(s)

* The cNX category is used sparingly in cases where regional lymph nodes have previously been surgically removed or where there is no documentation of physical examination of the axilla.

** cN1mi is rarely used but may be appropriate in cases where sentinel node biopsy is performed before tumor resection, most likely to occur in cases treated with neoadjuvant therapy.

Regional Lymph Nodes- Pathological (pN)

- pNx** Regional lymph nodes cannot be assessed (e.g., not removed for pathological study or previously removed)
- pN0** No regional lymph node metastasis identified or ITCs only

pN0(i+) ITCs only (malignant cell clusters no larger than 0.2 mm) in regional lymph node(s)

pN0(mol+) Positive molecular findings by reverse transcriptase polymerase chain reaction (RT-PCR); no ITCs detected

pN1 Micro metastases; or metastases in 1–3 axillary lymph nodes; and/or clinically negative internal mammary nodes with micro metastases or macro metastases by sentinel lymph node biopsy

pN1mi Micro metastases (approximately 200 cells, larger than 0.2 mm but none larger than 2.0 mm)

pN1a Metastases in 1–3 axillary lymph nodes, at least one metastasis larger than 2.0 mm

pN1b Metastases in ipsilateral internal mammary sentinel nodes, excluding ITCs

pN1c pN1a and pN1b combined

pN2 Metastases in 4–9 axillary lymph nodes; or positive ipsilateral internal mammary lymph nodes by imaging in the absence of axillary lymph node metastases

pN2a Metastases in 4–9 axillary lymph nodes (at least one tumor deposit larger than 2.0 mm)

pN2b Metastases in clinically detected internal mammary lymph nodes with or without microscopic confirmation; with pathologically negative axillary nodes

pN3 Metastases in –

pN3a Metastases in 10 or more axillary lymph nodes (at least one tumor deposit larger than 2.0 mm); or metastases to the infraclavicular (Level III axillary lymph) nodes

pN3b pN1a or pN2a (positive Level I, II axillary lymph nodes) in the presence of cN2b (positive internal mammary nodes by imaging); or pN2a in the presence of pN1b (more than three axillary lymph nodes and micro/macro-metastases by sentinel lymph node biopsy in clinically negative ipsilateral internal mammary lymph nodes)

pN3c Metastases in ipsilateral supraclavicular lymph nodes

Distant Metastasis (M)

M0 No clinical or radiographic evidence of distant metastases*

cM0(i+) No clinical or radiographic evidence of distant metastases in the presence of tumor cells or deposits no larger than 0.2 mm detected microscopically or by molecular techniques in circulating blood, bone marrow, or other nonregional nodal tissue in a patient without symptoms or signs of metastases

C1 Distant metastases detected by clinical and radiographic means

P1 Any histologically proven metastases in distant organs; or if in non-regional nodes, metastases greater than 0.2 mm

* Note that imaging studies are not required to assign the cM0 category

Stage/Prognostic Grouping

Stage 0 Tis N0 M0

Stage IA T1 N0 M0

Stage IB T0-1 N1mi M0

Stage IIA T0-1 N1 M0; T2 N0 M0

Stage IIB T2 N1 M0; T3 N0 M0

Stage IIIA T0-3 N2 M0

Stage IIIB T4 N0-2 M0

Stage IIIC Any T N3 M0

Stage IV Any T Any N M1

APPENDIX- VII

Percentage points or critical values of standard normal distribution (Z-distribution or Z table or Z_α table)

P-Value or level of significance(α)	Confidence level	Percentage point	
		One tail	Two tail
0.5(50%)		0.00	0.67
0.4(40%)		0.25	0.84
0.3(30%)		0.52	1.04
0.2(20%)	80% C. Level	0.84	1.28
0.1(10%)	90% C. Level	1.28	1.64
0.05(5%)	95% C. Level	1.64	1.96
0.02(2%)	98% C Level	2.05	2.33
0.01(1%)	99% C Level	2.33	2.58
0.005(0.5%)	99.5% C Level	2.58	2.81
0.002(0.2%)	99.7% C Level	2.88	3.09
0.001(0.1%)	99.9% C Level	3.09	3.29
0.0001(0.01%)	99.99% C Level	3.72	3.89

APPENDIX- VIII

Critical Values (Z_β) of Standard Normal Distribution (Z-Distribution) at Different Power

Power	B (Type-II error)	Z_β
0.70	0.30	0.52
0.80	0.20	0.84(0.85)
0.90	0.10	1.28
0.95	0.05	1.64
0.99	0.01	2.33

APPENDIX – XI

HELSINKI DECLARATION:

Clinical trial involving human subjects-to indicate whether the procedures followed were in accordance with the ethical standard of responsible committee or with the Helsinki declaration of 1975, as revised in 2013.

1. Direct student should not be included in the clinical trial / research.
2. Children should not be included (unless benefit will be obtained by the children).
3. Prisoners, pregnant women and acutely ill patients should not be included.
4. Patients should not be deprived of their basic human right.
5. Patient's name, initials or hospital numbers should not be used.
6. Informed written consent of the patient should be taken after explaining the objective, risk and benefit of the experiment.
7. No incentive cash or kind for healthy volunteer should be allowed.
